4. INVESTIGATIONAL PLAN

4.1. Study Design

4.1.1. Overview and Schema

This is an open label, Phase 1, non-randomized, safety, PK, and Pd study of IMGN853 in adult patients with solid tumors that have relapsed, and are refractory to standard therapies. The estimated study duration is approximately 50 months for patient accrual, dosing, and follow up. The study will be conducted in 2 stages: dose escalation and dose expansion. Two dosing schedules will be evaluated in this study:

Schedule A: IMGN853 administered on Day 1, with cycles repeating every 21 days (Q3W)

Schedule B: IMGN853 administered on Days 1, 8, and 15, with cycles repeating every 28 days (modified weekly schedule)

- Approximately 209 patients* will be enrolled in the study.
- Dose Escalation Phase: (1) Schedule A: 44 patients (2) Schedule B: 25 patients
- **Dose Expansion Cohort 1:** Patients with Epithelial Ovarian Cancer (EOC) which is resistant to platinum-based therapy 40 patients
- **Dose Expansion Cohort 2:** Advanced or recurrent uterine cancer 20 patients
- **Dose Expansion Cohort 3:** Patients with relapsed EOC 20 patients
- **Dose Expansion Cohort 4**: Relapsed/refractory NSCLC adenocarcinoma or bronchioloalveolar carcinoma (BAC) 20 patients
- **Dose Expansion Cohort 5:** Patients with Epithelial Ovarian Cancer (EOC) which has relapsed following platinum-based therapy 40 patients; patients enrolled into this cohort will self-administer daily corticosteroid eye drops to assess whether prophylaxis with topical steroids prevents or lessens severity of keratopathy and/or blurred vision.**NOTE:* Every effort will be made to ensure the requisite number of patients are accrued in each cohort, and to this end, communications with the site will be monitored carefully. There are instances however, where, as a result of simultaneous screening activities, patients may qualify for the study at the same time, resulting in slight over-enrollment in individual cohorts

The primary aim of the dose-escalation phase is to evaluate the safety and tolerability of IMGN853, to identify the MTD, and to characterize the PK profile of IMGN853.

Schedule A - once the MTD has been identified, enrollment to MTD Expansion Cohorts 1 and 2 will begin.

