10.5. Even-Numbered Cycles (2, 4, 6, etc.), End of Cycle

- Pregnancy test (may be performed more frequently in accordance to institutional requirements) (Appendix A and Appendix B)
 - o **Schedule A** − Day 18±3 days
 - Schedule B Day 21±3 days
- For patients who experience ocular toxicity and those who experience blurred vision but have normal eye examinations: complete ophthalmic examination (Section 5.8.8); to be performed by a board-certified ophthalmologist prior to the start of every other cycle from the time it is first reported.
- Tumor assessments by CT scan (Appendix A and Appendix B)
 - **Schedule A** Every 6 weeks±1 week

- o **Schedule B** − Every 8 weeks±1 week
- CA125 for patients with EOC, primary peritoneal cancer, fallopian tube cancer or uterine cancer (Appendix F) should be scheduled to coincide approximately with the radiographic tumor assessments

NOTE: Patients experiencing CA125 response must have a confirmatory test performed 28 days after initial response is documented.

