10.8. Follow-up Assessments

Safety Follow-up: A safety follow-up visit will occur 28 days (+ 14 days) after the last treatment. During this visit, the following assessments will be performed.

- Complete physical examination (Appendix A and Appendix B)
- Vital signs (Section 8.6, Appendix A and Appendix B)
- Pulse oximetry (Section 8.8)
- Weight (Appendix A and Appendix B)
- ECOG performance status (Appendix A and Appendix B)
- 12-Lead ECG (if clinically indicated)
- Pregnancy test for WCBP (Appendix A and Appendix B)
- Clinical laboratory tests (Section 8.10, Appendix A and Appendix B):
 - Serum chemistry
 - Hematology
 - Coagulation profile
 - Urinalysis
- Radiologic imaging to monitor tumor response if PD has not been documented already (Appendix A and Appendix B)
- For patients with EOC, uterine cancer or NSCLC only:
- CA125 for patients with EOC, primary peritoneal cancer, fallopian tube cancer or uterine cancer (Appendix F)

NOTE: patients experiencing CA125 response must have a confirmatory test performed at least 28 days after initial response is documented.

- AEs and SAEs (Appendix A and Appendix B)
- Ocular symptom assessment (Section 5.8.8)

ImmunoGen, Inc. Confidential Page 104 of 138

- Complete ophthalmic examination for all patients; alternatively, the complete examination can be performed at the End of Study visit.
 - Patients experiencing an ocular treatment-emergent adverse event (Section 5.8.8.2) will continue to have examinations every 2 weeks until the condition resolves or is deemed to be irreversible by the investigator.
- Concomitant medications(Appendix A and Appendix B)
- Directed neurological examination will be performed, to include light touch, pinprick, proprioception, and deep tendon reflexes (DTRs) of the upper and lower extremities; and questioning for symptoms of paresthesia and numbness. If abnormal, an NCI CTAE grade will be recorded and if warranted a neurologist will be consulted (Appendix A and Appendix B)
 - o Neurotoxicity Questionnaire (FACT/GOG NTx), Version 4.0 (Appendix G)
- HAHA and HADA sample collection as outlined in Section 6 and Appendix C

All serious adverse events, and those adverse events assessed by the Investigator as at least possibly related to study drug should continue to be followed until they resolve or stabilize, whichever comes first.

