Response Follow-up: Patients who have discontinued study treatment for reasons other than PD will be followed per Revised Response Criteria (RECIST 1.1, see Appendix E) every 12 weeks (+/- 3 weeks) until documentation of PD, or until the patient starts subsequent anti-cancer therapy, whichever comes first.

ImmunoGen, Inc. Confidential Page 105 of 138

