5. EFFICACY ANALYSES

Efficacy analyses will use data from the Response-Evaluable population unless otherwise specified. Unless stated otherwise, patients will be analyzed in the following groups: Escalation Schedule A, Escalation Schedule B, EOC Expansion Cohorts, Endometrial Expansion Cohort.

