5.1.3. Progression Free Survival (PFS)

PFS is defined as the time from the date of the first dose of study drug until the date of progressive disease or death from any cause, whichever occurs first. PFS is defined based on radiological assessments and determined by the investigator. Clinical progression is not considered a progression endpoint. PFS will be calculated using the following:

- Patients who did not die or have PD will be censored at the date of their last radiological assessment.
- Patients who had PD or death after missing two or more consecutive radiological assessments (PD or death date – last radiological assessment date +1 >=105 days) will be censored at the last adequate radiological assessment.
- Patients who had no baseline or post-baseline radiological assessment(s) will be censored on Day 1 unless the patient died within 105 days of Day 1; in that case, the patient will be considered as having an event at the date of death.
- Patients who started a new anti-cancer therapy prior to documented PD or death will be censored at the last radiological assessment prior to initiation of new anti-cancer therapy.
- When an analysis cutoff date is implemented, only data (deaths and radiological assessments) occurring on or prior to the cutoff date will be used for analysis.

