5.1.5. Time to Progression

Time to progression (TTP) is defined as the time from the date of the first dose of study drug until the date of progressive disease. TTP is defined based on radiological assessments and determined by the investigator. Clinical progression is not considered a progression endpoint. TTP will be censored as follows:

- Patients who did not have PD will be censored at the date of their last radiological assessment.

- Patients who had PD after missing two or more consecutive radiological assessments (PD date – last radiological assessment date +1 >=105 days) will be censored at the last adequate radiological assessment.
- Patients who had no baseline or post-baseline radiological assessment(s) will be censored on Day 1.
- Patients who started a new anti-cancer therapy prior to documented PD will be censored at the last radiological assessment prior to initiation of new anti-cancer therapy.
- When an analysis cutoff date is implemented, only radiological assessments occurring on or prior to the cutoff date will be used for analysis.
- Patients who died prior to PD will be censored at the last radiological assessment.

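### The SAP's 105-day test for two missed scans fits the 6-week on-treatment calendar, but on Schedule B and in 12-week follow-up it also censors progression found after one missed scan

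*SAP*

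**What the plan says.** The second censoring bullet for PFS (SAP 5.1.3) applies to patients whose progression or death comes "after missing two or more consecutive radiological assessments (PD or death date – last radiological assessment date +1 >=105 days". The matching bullet for TTP (SAP 5.1.5) reads "Patients who had PD after missing two or more consecutive radiological assessments (PD date – last radiological assessment date +1 >=105 days". Both censor at the last adequate scan. The SAP does not derive the 105 days and does not vary the limit by schedule or study phase.

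The protocol sets three scan intervals:

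- Schedule A on treatment (Protocol 10.5): "Every 6 weeks±1 week".
- Schedule B on treatment (Protocol 10.5; Appendix B agrees): "Every 8 weeks±1 week".
- Patients off drug without progression, either schedule (Protocol 10.8): "every 12 weeks (+/- 3 weeks) until documentation of PD".

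SAP 5 reports efficacy by "Escalation Schedule A, Escalation Schedule B, EOC Expansion Cohorts, Endometrial Expansion Cohort", so Schedule B gets its own PFS and TTP medians. Planned escalation numbers in Protocol 4.1.1 are "1) Schedule A: 44 patients (2) Schedule B: 25 patients".

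**The concern.** The bullets state a rule in words and then define it by a number. The number can agree with the words on one scan interval only. With longer intervals, a patient who missed one scan, or none, can pass the 105-day mark and be treated as having missed two. An observed progression then becomes a censored time at the previous scan.

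This tends to lengthen PFS and TTP, mostly late in the curve. The tables would also be described as censoring for two missed scans when that is not what was done.

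**Working it through.** **Inputs.** Intervals and windows in days: Schedule A 42±7, Schedule B 56±7 (Protocol 10.5), follow-up 84±21 (Protocol 10.8). The baseline scan is taken up to 28 days before first dose (Protocol 8.13). The SAP adds 1 to the gap, so a progression is censored when the gap is at least 104 days.

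**The plan's own figure.** 105 days is 15 weeks = 2 × (6+1) + 1 weeks. It is also the midpoint of the nominal 6-week gaps after one and two missed scans: (84 + 126)/2 = 105. It therefore looks built for the 6-week calendar.

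**Gaps between scans.** With m scans missed and both scans free to move around fixed dates, gap = (m+1) × interval ± 2 × window. The share censored assumes whole days, uniform and independent within the windows.

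| Calendar | None missed | One missed | Two missed |
|---|---|---|---|
| Schedule A | 28–56 (0%) | 70–98 (0%) | 112–140 (100%) |
| Schedule B | 42–70 (0%) | 98–126 (91%) | 154–182 (100%) |
| Follow-up | 42–126 (15%) | 126–210 (100%) | 210–294 (100%) |

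- Schedule B, one missed: the gap is below 104 only if the second scan falls at least 9 days earlier, relative to its date, than the first. That is 6+5+4+3+2+1 = 21 of 15 × 15 = 225 combinations, so 204/225 = 91% are censored. If the window runs from the previous scan instead, the gap is 112±7 = 105–119 and all are censored.
- Follow-up, none missed: on fixed dates, 276 of 43 × 43 = 1,849 combinations reach 104 days (15%). With the window run from the previous scan, the gap is 63–105 days and 2 of 43 days qualify (5%).

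**First on-study scan missed, progression at the second.** The gap runs from the baseline scan, taken 1–28 days before Day 1.

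- Schedule A: 84 + (1 to 28) ± 7 = 78–119 days. Censored: 135 of 28 × 15 = 420 combinations (32%) if baseline scans are spread over 28 days; 3 of 14 × 15 = 210 (1%) if all fall within 14 days.
- Schedule B: 112 + (1 to 28) ± 7 = 106–147 days, always censored.

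**Limits that would match the words (on gap + 1).**

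- Schedule B: any value from 128 to 155 lies above the largest one-missed value (127) and at or below the smallest two-missed value (155). The construction 2 × (8+1) + 1 weeks gives 133.
- Between two follow-up scans: 212 censors no one-missed gap (largest 211) and 1,848 of 1,849 two-missed combinations.
- Counting from Day 1 when only a baseline scan exists: Schedule A second scan at days 77–91, third at 119–133; Schedule B 105–119 and 161–175. Limits of 105 and 133 then separate one from two missed.

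**Where 212 fails: the first gap after treatment ends.** Suppose the 12 weeks run from the end-of-treatment visit, the last scan was L days before it, and the first follow-up scan is missed. The gap is 168 + L ± 21. If the appendix footnotes allow the end-of-treatment and 28-day-visit scans to be skipped, and the visits are 14 days apart, L can reach 42 − 14 = 28 (A) or 56 − 14 = 42 (B). The gap then reaches 217 or 231 days. With L uniform over 0–42 or 0–56, a limit of 212 would still censor 28/1,849 = 1.5% (A) and 231/2,451 = 9.4% (B) after one missed scan. If a scan is always done at the end-of-treatment visit, L = 0, the gap is 147–189 and the problem disappears.

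**Effect on summaries.** A simulation compared the 105-day rule with a count of missed scans (20,000 patients per setting, 16 settings per schedule). It assumed a median time to progression of 4–6 months, 5–15% of scans missed, 10–25% stopping drug without progression, a 28-day visit 14 days after end of treatment with its scan always or conditionally done, and follow-up capped at one year. Deaths were not modelled. The median moved 0–2 days on Schedule A in 15 of 16 settings (at most 4), and 0–7 days on Schedule B in 14 of 16 (17 and 47 in the other two). The 12-month rate rose by 0.4 to 2.2 points on A and 1.4 to 6.9 on B.

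**The case against.** The strongest defence is that the documents support a 6-week calendar for everyone. Protocol Appendix E gives scans every 6 weeks (±1) with no split by schedule, and SAP 5.1.1 derives its 35-day minimum for stable disease from the same interval. This explains the 105 days, and it means the Schedule B part rests on a conflict within the protocol. It does not remove that part: Section 10.5 and Appendix B give 8 weeks specifically for Schedule B, and every second 28-day cycle (Protocol 8.13) is also 8 weeks. The follow-up part does not depend on this conflict.

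It can also be said that the formula governs, so programming is unambiguous; that the study has no formal hypothesis testing; that Schedule B is closed to new patients; and that SAP 5.2.8 already lists censoring. All true, and they limit the weight of the point. The listing would identify affected patients, but the tables would still follow the 105-day rule.

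Finally, a count of missed scans is itself a convention. Dating progression at detection after a long gap also places it late. The complaint is that the number contradicts the stated rule, not that the count recovers the true progression date.

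A reader might infer that PFS in the expansion cohorts is materially inflated. The documents do not support that. Those cohorts use Schedule A, where the rule works between on-treatment scans. They are exposed only through off-drug follow-up and a missed first scan, and the simulated shift in the median is small.

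**Conclusion.** The point holds as a mismatch between the rule's words and its number, of minor to moderate weight. The limit is sound between on-treatment scans on Schedule A. It is too short on Schedule B (about 91% of progressions after one missed scan censored) and in follow-up (100% after one missed, about 5% to 15% after none). It also misfires when the first on-study scan is missed: always on Schedule B, in 1% to 32% of cases on Schedule A depending on when baseline scans are taken.

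The ranges follow from the protocol's windows. The percentages also need the uniform-window assumption, and the Schedule B figures need the 8-week interval. They are shares of progressions found after the stated number of missed scans, not of all patients. How many patients are affected depends on how often scans are missed, which the documents do not give; the simulation shows order of magnitude only.

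It would also be too much to infer that every 105-day limit in the SAP is wrong. Those counted from first dose (third PFS bullet and SAP 3.7.2) make no claim about missed scans and need no change on this ground.

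**What to change.** In the second bullets of SAP 5.1.3 and 5.1.5, replace the day limit with a count of missed scheduled scans on the calendar in force for each patient: 6 weeks on Schedule A, 8 weeks on Schedule B, 12 weeks off drug. Count from Day 1 when only a baseline scan exists.

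If a day limit on gap + 1 is kept, use 105 on Schedule A treatment, a value from 128 to 155 (for example 133) on Schedule B treatment, and 212 only between two follow-up scans. Use the count for the first gap after treatment ends.

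Three points need settling so that the count is defined:

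- The date from which the 12 weeks run.
- Whether scans at the end-of-treatment and 28-day visits are scheduled scans. Protocol 10.7 and 10.8 list imaging with no exception for a recent scan (10.8: "Radiologic imaging to monitor tumor response if PD has not been documented already"), while the Appendix A and B footnotes waive it if one was done in the previous 6 or 8 weeks. These must be reconciled.
- The Schedule B interval: Appendix E against Section 10.5 and Appendix B.

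A sensitivity analysis counting all progressions and deaths as events would be useful but is optional. The cost is wording in two bullets, clarification of the scan calendar and programming of the count. No new data are needed, and SAP 1.1 allows changes until database lock.

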8.13. Radiologic Imaging

Radiographic tumor evaluation by computed tomography (CT) or MRI of chest, abdomen, and pelvis (EOC patients only) will be performed within 28 days prior to first dose and approximately every second cycle, from the date of first dose until the 28-day Follow-up visit. The same radiographic assessment used at screening must be used at all subsequent radiographic evaluations.

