8.14. Tumor Response Assessment

Tumor response for patients with measurable lesions should be assessed using RECIST 1.1 (Eisenhauer 2009, Appendix E). Patients with ovarian and uterine cancer will have CA125 measured at approximately the same time they undergo radiologic assessment. Patients will have a baseline tumor assessment done within the 28 days prior to Cycle 1, Day 1. Patients with measurable lesions should be assessed using CT scan approximately every second cycle, from the date of first dose until the 28-day Follow-up visit. Although progression may be determined by the investigator based upon clinical deterioration, every effort should be made to document progression using radiographic methods. The basis for determination of progression per clinical deterioration should be documented.

Patients experiencing CA125 response must have a confirmatory test performed at least 28 days after initial response is documented. In the case of stable disease (SD), follow-up measurements must have met the SD criteria at least once after study entry at a minimum interval of 6 weeks.

Electronic copies of radiologic images with tumor size measurements, including baselines assessment, must be sent to the sponsor within 4 weeks after PR/CR has been documented, together with a copy of the corresponding radiology report and tumor assessment worksheets. Scans must be in Digital Imaging and Communications in Medicine (DICOM) format. Electronic transfer of scan files (via FTP, HTTP, or similar means) is preferred, although transfer on physical media (such as DVD or CD) is acceptable. For digital media, one time point/patient/disk is expected. The site is expected to maintain a copy of digital data for the retention period applicable to the protocol, Good Clinical Practices (GCP), and federal, international, and/or state legal and medical requirements. ImmunoGen will retain the media for

ImmunoGen, Inc. Confidential Page 88 of 138

a period of 2 years following the date a marketing application is approved or, if no application is to be filed or if the application is not approved for such indication, until 2 years after the investigation is discontinued.

Note: It is very important that the same method of radiologic assessment be used throughout the study and that the same lesions are followed.

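### The 105-day gap rule for PFS and TTP can start from a pre-dose baseline scan, so some events from Day 77 on can be censored before time zero depending on when the screening scan was done

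*SAP*

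**What the plan says.** PFS and TTP both start at the first dose (SAP 5.1.3 and 5.1.5), and Protocol 11 sets Cycle 1, Day 1 as the start time for all efficacy analyses.

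The second bullet of SAP 5.1.3 covers PD or death "after missing two or more consecutive radiological assessments" and gives the working condition in parentheses: "PD or death date – last radiological assessment date +1 >=105 days) will be censored at the last adequate radiological assessment". The second bullet of SAP 5.1.5 repeats it for PD: "PD date – last radiological assessment date +1 >=105 days) will be censored at the last adequate radiological assessment".

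The third bullet of 5.1.3 begins "Patients who had no baseline or post-baseline radiological assessment(s) will be censored on Day 1" and continues "unless the patient died within 105 days of Day 1; in that case, the patient will be considered as having an event", dated at the death. The third bullet of 5.1.5 also censors on Day 1 but has no exception for death, because death is not a TTP event.

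On the baseline scan, Protocol 8.13 says that imaging "will be performed within 28 days prior to first dose", and Protocol 8.14 says "Patients will have a baseline tumor assessment done within the 28 days prior to Cycle 1, Day 1". The SAP gives no order of precedence between the bullets and does not make Day 1 the earliest possible censoring date.

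**The concern.** The third bullet of 5.1.3 itself treats a baseline scan as a radiological assessment. For a patient with no post-baseline scan before the event, the last assessment in the gap formula is therefore the screening scan, taken before the clock starts. The formula then adds pre-dose days to the gap and sends the censoring date back to a point before time zero.

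Two things are at stake. First, an event can become a zero or negative time, which contributes nothing to a Kaplan-Meier risk set. Second, two patients with the same course after dosing can be handled differently because one was scanned earlier in screening. For PFS deaths, the second and third bullets may also give opposite answers.

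**Working it through.** **Inputs.** The threshold is 105 days (SAP 5.1.3, 5.1.5). The baseline scan is k days before Day 1, with k = 0 to 28 (Protocol 8.13, 8.14). Schedule A scans are every 6 weeks ± 1 week (Protocol 10.5, Appendix A), so the first is nominally on Day 43 (window 36-50) and the second on Day 85 (window 78-92). The SAP gives no derivation of 105, so there is no figure to reproduce. For reference, 2 × 42 + 21 = 105, while two intervals at the outer window are 2 × 49 = 98.

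**Formula.** Study day d lies d - 1 days after Day 1. The date difference from the baseline scan is (d - 1) + k, and the SAP adds 1, which gives d + k. The rule is met when d + k >= 105, that is, from Day 105 - k.

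**(a) PFS deaths with no post-baseline scan.** The third bullet's limit is Day 105. Deaths up to Day 105 that the second bullet also catches on Schedule A are:

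| k | Formula alone | Formula, and both scan windows closed (after Day 92) |
|---|---|---|
| 28 | Days 77-105 (29 days) | Days 93-105 (13) |
| 21 | Days 84-105 (22) | Days 93-105 (13) |
| 14 | Days 91-105 (15) | Days 93-105 (13) |
| 7 | Days 98-105 (8) | Days 98-105 (8) |
| 1 | Days 104-105 (2) | Days 104-105 (2) |
| 0 | Day 105 (1) | Day 105 (1) |

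With k = 28 the second bullet censors such a death 28 days before Day 1. What the third bullet does depends on its *or*:
- If it means that either scan is missing, the death is an event at its own date and the two bullets conflict.
- If it means that neither scan exists, the third bullet does not apply. The death is censored before dosing, yet the same death in a patient with no scan at all is an event.

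On Schedule B (every 8 weeks ± 1 week) the second window closes on Day 1 + 112 + 7 = 120, so under the stricter reading no death by Day 105 is caught.

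**(b) PD on Schedule A, with baseline as the last scan before PD.**
- At the first scheduled scan, the largest value is 50 + 28 = 78, so the rule is never met.
- At the second scheduled scan after one missed scan, the rule is met on Day 78 if k >= 27, on Day 85 if k >= 20 and on Day 92 if k >= 13.
- For PD on Day 85, k = 28 gives 113 (censored before Day 1) and k = 1 gives 86 (an event).

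In this case only one scan was missed, so the formula and the bullet's own words disagree.

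**Effect of one patient (illustration).** Assume no other censoring and half of the group event-free at some time after d. Removing one event moves 50/100 to 50/99 = 50.5% in the pooled EOC cohorts (40 + 20 + 40 planned), and 10/20 to 10/19 = 52.6% in the endometrial cohort of 20.

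**The case against.** The best defence is that the words govern: the second bullet applies only after two or more missed assessments, and the parenthesis merely expresses that. PD at the second scheduled scan after one missed scan would then not be caught, nor would a death on Day 85. This has force, but a programmer will code the formula, and the SAP does not say that both conditions must hold. If both must hold, (b) disappears, but a baseline-only death on Schedule A on about Days 93-105 still meets both when k >= 12.

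A second defence is that the third bullet is the specific rule for these deaths. It is anchored on Day 1, and SAP 3.7.2 keeps deaths within 105 days of first dose in the Response-Evaluable population. That is good evidence of intent. It does not settle the matter, because no precedence is stated and, read as neither scan, the bullet does not reach a patient who has a baseline scan.

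Finally, PFS and TTP are secondary, no formal hypothesis is tested, and censoring is listed by patient (SAP 5.2.8), so a negative time could be noticed. That limits the consequence but does not correct the rule.

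Some stronger inferences are tempting but unsupported:
- **That the earliest failures are lost.** Nothing before Day 77 meets the rule, and PD at the first scheduled scan always stays an event.
- **That a PD patient can have only a baseline scan.** PD must be radiological under 5.1.3 and 5.1.5. Baseline can only be the last scan *before* PD.
- **That PD or TTP contradicts the third bullet.** The exception there concerns PFS deaths only.
- **That the k thresholds are shares of patients.** That would need the distribution of screening-scan dates, which the documents do not give.

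**Conclusion.** The point holds in a limited form. As written, the formula can start from a scan up to 28 days before dosing, censor a death or PD before time zero, and let the screening date decide the outcome. The reach is d + k >= 105: Days 77-105 for baseline-only PFS deaths at k = 28, narrowing to about Days 93-105 on Schedule A if two windows must also have been missed, and shorter still for small k. For PD at the Day 85 scan after one missed scan, k >= 20 is needed and the formula must be applied without the verbal condition. A direct contradiction between the second and third bullets exists only for PFS deaths and only if *or* means either scan is missing; on the other reading the fault is inconsistent treatment of the same death.

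Few patients should be affected, since each must lack an earlier post-baseline scan and fail in a narrow range of days; the documents give no count. The primary endpoints, MTD and RP2D, are untouched. It still merits correction, because a stated rule gives a wrong result and PFS curves are planned in small crossed subgroups (SAP 5.2.7), where one event can show.

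**What to change.** In SAP 5.1.3 and 5.1.5:

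1. Count the gap from the later of Day 1 and the last adequate radiological assessment.
2. State that no PFS or TTP censoring date precedes Day 1. This also covers the first and fourth bullets of both sections and the last TTP bullet (death before PD), which can likewise fall back on a baseline scan.
3. State that patients with no post-baseline assessment follow the third bullet only. In PFS, death within 105 days of Day 1 is then an event and overrides the second bullet. In TTP these patients are censored on Day 1.

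With step 1, when the baseline scan is the last scan, the quantity becomes (d - 1) + 1 = d. The rule is then first met on Day 105 whatever k is, and PD on Day 85 or Day 92 stays an event. The remaining overlap with the third bullet is Day 105 alone (two days if the limit is read as a date difference), and step 3 resolves it.

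The cost is a few sentences and a small change to the derivation program. SAP 1.1 allows changes until database lock. The only downside is that PFS may look slightly less favourable.
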